- decreased from 184 to 163 mg/dL (P=0.01). Median time >250 mg/dL decreased by more than
- one hour per day. Median time <54 mg/dL was 0.00% at baseline and during CIQ use (IQR -
- 60 0.02% +0.02%). Median time in closed loop was 96% (interquartile range 93% to 96%). There
- were no severe hypoglycemia or DKA events. On the Diabetes Impact and Device Satisfaction
- 62 Scale, participants indicated a high level of satisfaction with CIQ (mean item score 8.8±1.9 on
- scale of 1-10). Both prior MDI or pump and prior basal insulin only participants showed similar
- levels of improvement in all outcomes.

65

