1452 1453 1454 1455 1456 1457 1458 1459	CGM-measured prolonged hyperglycemia events are defined as ≥90 cumulative minutes with CGM glucose >300 mg/dL within a 120-minute period (the participant becomes eligible for another prolonged hyperglycemia event after the CGM glucose is <180 mg/dL for ≥15 consecutive minutes). CGM-measured hypoglycemia events are defined as ≥15 consecutive minutes with CGM glucose <54 mg/dL (the participant becomes eligible for another hypoglycemia event after the CGM glucose is ≥70 mg/dL for ≥15 consecutive minutes). For each of these metrics, the number of events per week is calculated for each participant and each metric is then analyzed as a continuous variable as described below.
1460 1461 1462 1463 1464 1465 1466 1467	Summary statistics (mean \pm SD or median (quartiles)) will be reported for the CGM-measured metrics at baseline and during follow up as well as for differences from baseline by treatment group. CGM metric differences between AID and Control Groups will be compared using a linear mixed effects regression model adjusting for the baseline value of the metric and clinical center (random effect). A separate variance will be modelled for each group. Residual values will be examined for an approximate normal distribution. If residuals are highly skewed, then a transformation or robust statistical method (e.g., non-parametric or MM estimation) will be used instead. Missing data will be handled using direct likelihood.
1468	11.7.2 Binary Outcomes
1469 1470 1471 1472	For the binary HbA1c outcomes, risk-adjusted percentages by treatment group will be computed at 13 weeks from a logistic regression model. The logistic regression will adjust for baseline HbA1c (as a continuous factor) and clinical site using generalized estimating equations (GEE). Similar analyses will be done for the binary CGM outcomes.
1473	11.8 Questionnaires and Other Outcomes Analyses
1474 1475 1476 1477	For questionnaires administered to both randomization groups, comparisons will be made using similar linear models as described above for the primary and key secondary outcomes. If questionnaires include a total score, separate models will be run for the total score and selected subscales.
1478 1479	Similarly, for insulin, weight and BMI metrics comparisons will be made using similar linear models as described above for the primary HbA1c analysis.

1480	11.9 Safety Analyses

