- Thirteen Weeks of Follow-up: All CGM data following the randomization will be included. 223 • Since the meal and exercise sessions are designed as challenges to the system and the data to be 224 analyzed for possibly induced safety events, the CGM data between the start of the meal or 225 exercise and 6:00AM next morning will be analyzed separately (see Sections 5.4 and 5.5 below) 226 and not included here. If the 13-week visit is more than 13 weeks after the randomization visit 227 for a participant, then the CGM data will be truncated at 13 weeks (i.e., 91 days). At least 168hr 228 229 of data during these 13 weeks of follow-up are required for the glycemic metrics to be calculated 230 and for a participant to be included in the glycemic analyses. These are either Tandem pump CGM data or Dexcom CGM data if obtained to fill any Tandem data gaps. 231
- All CGM metrics during baseline and follow-up periods will be calculated giving equal weight to
   each sensor reading for each participant.
- Calculation of CGM metrics for the treatment group comparisons will exclude the challenges and the period through 6AM on the day following the end of the challenge. CGM metrics during and following the challenges will be reported separately as described in Sections 5.4. and 5.5; while an overall analysis will be performed for all CGM data in the AID group (i.e., including the challenge data) as described in Section 17.
- CGM-measured prolonged hyperglycemia events are defined as ≥90 cumulative minutes with CGM glucose >300 mg/dL within a 120-minute period (the participant becomes eligible for another prolonged hyperglycemia event after the CGM glucose is <180 mg/dL for ≥15

   consecutive minutes).
- CGM-measured hypoglycemia events are defined as ≥15 consecutive minutes with CGM glucose <54 mg/dL (the participant becomes eligible for another hypoglycemia event after the CGM glucose is ≥70 mg/dL for ≥15 consecutive minutes). For each of these metrics, the number of events per week is calculated for each participant and each metric is then analyzed as a continuous variable as described below.

- 248 249

257

258

259

260

261

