### 6. Description of Statistical Methods

- 350 351
- 352 6.1. General Approach:

- All analyses comparing the AID arm with Control arm will follow intention-to-treatment (ITT) 353 • approach, which means participants will be analyzed in the treatment arm assigned by 354 randomization regardless of the actual system use. All randomized participants with any data will 355 be included in the primary analysis and secondary analyses. 356 In the unlikely event that an enrolled participant is later found to be ineligible, the participant 357 • will be excluded from all analyses. 358 • All covariates obtained on a continuous scale will be entered into the models as continuous 359 variables unless it is determined that a variable does not have a linear relationship with the 360 outcome. In such a case, categorization and/or transformation will be explored. 361 All p-values will be two-sided. 362 • Standard residual diagnostics will be performed for all analyses. If values are highly skewed, 363 then a nonparametric or robust regression using M-estimation will be used instead for the 364 primary and secondary outcomes. Previous experience suggests that no transformation, 365 366 nonparametric, or M-estimation analyses will be necessary for HbA1c, mean glucose, % time in range 70-180 mg/dL, or % above 180 mg/dL. Other outcomes like % below 54 mg/dL will likely 367 be skewed with a need for a transformation, nonparametric, or M-estimation. 368 369 370 **6.2 Analysis Cohorts** 371 372 373 Primary and Secondary Analyses: All randomized participants with any data will be included in the primary and secondary analyses. 374 • Any partial data (i.e., missing baseline or follow-up) will be handled using the maximum likelihood 375 method (see Section 7 below). 376 377 • All participants with at least one meal challenge and with the minimum amount of CGM data during these periods – as defined above in Section 5.4 - will be included in the corresponding meal analysis. 378 Similar for participants with at least one scheduled exercise and the exercise analyses. 379 380 381 Per Protocol (PP) Analyses: Per-protocol analyses will be performed for primary outcome and secondary hierarchical outcomes (see 382 Section 8.2 below) only if >5% of participants will be excluded. All of the following criteria must be 383 met for a participant to be included in the per-protocol analyses. The criteria are as follows: 384 385 • 13-week visit completed,
- No major protocol deviations, and

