### 420 8.1 Secondary CGM Metrics

Summary statistics (mean ± SD or median (quartiles)) will be reported for the CGM-measured metrics at baseline and during follow up as well as for differences from baseline by treatment group. CGM metric differences between AID and Control Groups will be compared using a linear mixed effects regression model adjusting for the baseline value of the metric and clinical center (random effect). A separate variance will be modelled for each group. Residual values will be examined for an approximate normal distribution. If residuals are highly skewed, then a transformation or robust statistical method (e.g., nonparametric or M-estimation) will be used instead. Missing data will be handled using direct likelihood.

428 429

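### M-estimation should not remain a fallback for time <54 mg/dL and CGM hypoglycaemia events: with many zeros it can shrink the difference and give invalid p-values

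*SAP*

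**What the plan says.** The default for every CGM metric is a linear mixed model with baseline value, random centre and a separate variance per arm (SAP 8.1). The fallback is described in several places:

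- SAP 6.1: "If values are highly skewed", then "a nonparametric or robust regression using M-estimation will be used instead" for primary and secondary outcomes. It predicts which outcomes will need this: "Other outcomes like % below 54 mg/dL will likely" "be skewed with a need for a transformation, nonparametric, or M-estimation".
- SAP 8.1: "If residuals are highly skewed, then a transformation or robust statistical method" applies, with nonparametric and M-estimation given as examples.
- Protocol 11.7.1: a "transformation or robust statistical method (e.g., non-parametric or MM estimation) will be used". The estimator named is MM, not M.
- SAP 5.3: hypoglycaemia and prolonged hyperglycaemia events become events per week, and "each metric is then analyzed as a continuous variable". They therefore inherit the same model and fallback.

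Neither document says which option applies, or gives the weight function, tuning constant, scale estimator or target quantity. In the fixed sequence of SAP 8.2, time <54 mg/dL is eighth of ten and hypoglycaemia events ninth. Both are also safety measures (SAP 5.2 and 9).

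The only evidence on zeros is the pilot in Protocol 1.3: "Median time <54 mg/dL was 0.00% at baseline and during CIQ use".

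**The concern.** M-estimation suits roughly symmetric data with a few stray values. These two endpoints are different: many participants may sit at zero, and the large values are the hypoglycaemia the trial wants to measure. A method that discounts large residuals then discounts those participants.

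Two things follow. The estimate moves away from the difference in means, which matters most if the AID arm has an excess. And once more than half the residuals are close to zero, the usual scale estimate, based on the median absolute residual, can fall towards zero. The standard error is built on that scale, so the p-value loses its meaning. A fixed-sequence procedure holds its error rate only if each test in it has its stated level.

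**Working it through.** **The plan's own figure.** The only power statement is for HbA1c (SAP 4). Residual SD = 1.0 × √(1 − 0.3²) = 0.954. With 100 and 200 completers, SE = 0.954 × √(1/100 + 1/200) = 0.1168. For 0.38: 0.38/0.1168 − 1.96 = 1.29, so power is 90.2%. For 0.35 and 0.33 it is 85.0% and 80.6%. The stated 90%, 85% and 80% are reproduced, which confirms the 100:200 layout used below. No figure is given for any hypoglycaemia endpoint.

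**How many zeros?** SAP 5.4 equates 2 hours with 24 readings, so one reading is 5 minutes. Six weeks is 42 × 1,440 = 60,480 minutes, so one low reading is 5/60,480 = 0.0083%, which rounds to 0.01%. If the pilot median was computed over all 30 participants and rounded to two decimals, at least 15 had no reading <54 mg/dL on Control-IQ. Missing data make a single reading a larger share, so this still holds. Over 13 weeks fewer people will stay at zero. An event needs at least 15 consecutive minutes <54 mg/dL, so its zero share is at least that of time <54. The documents support many zeros but give no share for this trial.

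**Mechanism.** A Huber fit gives residual r the weight min(1, k·s/|r|), where s is proportional to the median |r|. As s falls towards zero, so do the weights of participants with events. Bisquare gives zero weight beyond a fixed multiple of s.

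**Size of the shrinkage.** All rates below are assumed. There are 100 Control and 200 AID participants, with baseline adjustment, default tuning and a median-absolute-deviation scale. Entries are the M-estimate divided by the linear mean difference.

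| Scenario (zeros Control/AID) | Huber | Bisquare |
|---|---|---|
| Events 0.20/week doubled (28%/16%) | 0.73 | 0.60 |
| Events 0.10/week doubled (53%/40%) | 0.057/0.098 = 0.58 | – |
| Events 0.10/week doubled, more overdispersed (64%/54%) | 0.027/0.101 = 0.27 | – |
| Events 0.10/week halved (53%/65%) | 0.45 | 0.23 |
| Events 0.02/week halved (81%/89%) | 0.00 | 0.04 |
| Time <54, moderate skew (about 20%/40%) | 0.80 | 0.74 |
| Time <54, heavy skew (about 40%/60%) | 0.37 | 0.11 |
| Time <54, moderate skew (about 60%/80%) | 0.03 | 0.05 |

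Over all scenarios run, Huber ranged from 0.00 to 0.80 and bisquare from 0.01 to 0.74.

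**Validity with no true difference (nominal 5%).** Zero-inflated lognormal values, no covariate, 200 replicates:

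| Zeros | Linear | Rank | Huber | Bisquare |
|---|---|---|---|---|
| 30% | 4% | 5% | 5% | 4% |
| 50% | 4.5% | 6.5% | 5% | 23% |
| 60% | 4% | 5% | 5.5% | 51.5% |
| 80% | 3.5% | 4.5% | 24% | 47.5% |

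The Monte Carlo standard error is √(0.05 × 0.95/200) = 1.5 points at 5% and √(0.24 × 0.76/200) = 3.0 points at 24%. For event rates with a baseline covariate, Huber held about 6% up to about 65% zeros, then rejected 15% at 75% and 39-43% at 81%. Bisquare rejected 12% at 53% zeros and 37-50% from 60% to 81%, and gave no usable p-value in up to 14% of replicates. Rank and linear robust-variance tests stayed near 5%.

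**Effect on the hierarchy.** If the first seven nulls are false and rejected and the eighth is true, the chance of a false claim at that step is the level of that single test: 24% for Huber at 80% zeros, not 5%.

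**The case against.** The strongest reply is that nothing obliges the trial to use M-estimation. A transformation and a nonparametric method are also listed, and neither discounts participants with events in this way. The size of the effect rests wholly on assumed rates. That stands, and it limits the point to an option the plan should not keep open.

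Several stronger readings are tempting, and the documents do not support them:

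- *That the plan would understate a difference by about half.* No such figure can be derived. Half is one value in a range from about 20% to nearly all, and understatement presumes that the mean difference is the target, which the SAP does not say.
- *That all four low-glucose and event endpoints are affected.* Protocol 1.3 gives real-world time below range of 0.5% (IQR 0.2-1.0%) and time <70 mg/dL of 0.3% (IQR 0.1-0.6%) at 180 days. The lower quartiles are above zero, so time <70 is skewed but not shown to be zero-heavy. Nothing is given for prolonged hyperglycaemia events.
- *That power is the reason to change.* On event rates doubled from 0.10/week without covariates, Huber and rank power were 84% and 83% at 46% zeros, and 42% and 46% at 59%. Linear gave 95% and 81%, negative binomial 94% and 78%. The rank test is no better than Huber there. The case rests on bias and validity.
- *That an excess of hypoglycaemia would be hidden.* Arm summaries are reported for every hierarchical outcome (SAP 8.2), time <54 below 1% is analysed as a binary outcome (SAP 8.5), and severe hypoglycaemia is tested if at least 5 events occur (SAP 9).

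The pilot is also thin: 30 people over 6 weeks, 13 of them not using bolus insulin. Equal weighting of a participant with 168 hours of CGM and one with 13 weeks is real (SAP 5.3), but the linear mean difference was still recovered with 10% of participants on partial exposure.

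**Conclusion.** The concern holds for time <54 mg/dL and CGM-measured hypoglycaemia events. M-estimation is a listed fallback that the SAP expects it may need for time <54, and it is unsuitable when many values are zero. Under assumed rates it shrinks the mean difference by about 20% to nearly all. Default fits lose their level: about 15-45% null rejection for Huber at 75-81% zeros, and about 35-50% for bisquare at 60% or more. Huber is not invalid at every zero share; up to about 65% zeros it kept its level while still shrinking the estimate.

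This rests on assumed rates, zero shares and skew. Centre effects and separate variances by arm were not simulated. MM estimation was not run either; its high-breakdown scale can also be zero once more than half the residuals are, so I would not rely on it, but that is reasoning and not a result. The error reaches the hierarchy only if testing gets as far as the eighth endpoint.

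**What to change.** Before any outcome data are compared by arm:

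1. Remove M- and MM-estimation as options for time <54 mg/dL and CGM hypoglycaemia events in SAP 6.1 and 8.1.
2. Hypoglycaemia events: choose one analysis now. Either compare mean rates with robust variance, or fit a count model with a log CGM-time offset. Adjust for baseline rate and site, and state whether the target is a rate difference or a rate ratio.
3. Time <54 mg/dL: use a rank-based test that keeps the baseline adjustment and site, with the mean difference and a bootstrap 95% CI as a descriptive estimate.
4. Extend this to prolonged hyperglycaemia events only if blinded pooled data show many zeros. Leave time <70 mg/dL under the existing skewness rule.
5. Reconcile M-estimation (SAP 6.1, 7 and 8.1) with MM estimation (Protocol 11.6 and 11.7.1) wherever a robust fit is kept.

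The cost is SAP wording and small programming work. The downside is that the rank p-value and the mean-difference CI can disagree, so the SAP must state that the rank p-value decides the hierarchy.

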### 395 7. Primary Analyses

396

397 The primary endpoint for this study is HbA1c at 13 weeks adjusted for baseline HbA1c.

Summary statistics (mean  $\pm$  SD or median (quartiles) – appropriate to the distribution) will be reported for the baseline, 13 weeks values, and their differences.

HbA1c at 13 weeks will be compared between the AID and Control Groups using a linear mixed effects
regression model adjusting for baseline HbA1c and clinical center (random factor). A separate variance
will be modelled for each treatment group. HbA1c is expected to be normally distributed, but regression
diagnostics will be performed to check the residuals and an appropriate alternative transformation or
robust statistical method (e.g., non-parametric or M-estimation) will be performed if the residuals have a
skewed distribution.

In the event that some HbA1c values are not available at 13 weeks then the linear mixed effect
regression model will use the method of direct likelihood to incorporate information from baseline
measurements to calculate the maximum likelihood at 13 weeks. The method of direct likelihood will
function similarly in the event of missing HbA1c at baseline for a participant.

410 Only central lab HbA1c measurements will be used in the analyses.

411 Imbalances between groups in important covariates are not expected to be of sufficient magnitude to

412 produce confounding. However, the presence of confounding will be evaluated in the sensitivity

- analyses by including factors potentially associated with the outcome for which there is an imbalance
- 414 between groups (see Section 8.4 below).
- 415
- 416
- 417

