803 804 805	The study insulin will be shipped by the manufacturer, in coordination with the study Coordinating Center, directly to each clinical site for storage and dispensation to study participants.
806	• Formulation, Appearance, Packaging, and Labeling
807 808 809	The study insulin is a sterile, aqueous, clear, and colorless solution for subcutaneous or intravenous administration. Each mL contains 100 units of insulin aspart. Package labelling will be functionally identical to commercial drug.
810	Product Storage and Stability
811	Dispense in the original sealed carton with the enclosed Instructions for Use.

812 813 814 815	Refrigerate unopened study insulin vials between 36°F to 46°F (2°C to 8°C) until time of use and keep in the original carton to protect from light. Do not freeze or use study insulin if it has been frozen. Do not expose to direct heat. Discard opened or unopened study insulin vials stored at room temperature below 86°F (30°C) after 28 days.
816	Post-Study Disposal
817 818	At the conclusion of study activities, remaining unopened vials of study insulin will be disposed/destroyed by each clinical site in accordance with local disposal policies.
819	7.3 Study Device Accountability Procedures
820	Device and drug accountability procedures will be detailed in the site procedures manual.
821	7.4 Participant Access to Study Device at Study Closure
822 823 824	Participants will be returned to their pre-study insulin therapy at the conclusion of the study and must return study-assigned devices and unopened insulin to the clinical site as instructed by study staff.

825	Chapter 8: Testing Procedures and Questionnaires	
826	8.1 Laboratory Testing	
827	1. HbA1c:	
828 829 830 831	• HbA1c level measured using the DCA2000 or comparable point of care device or local lab at the Screening visit, if no comparable measurement is available within 30 days prior to enrollment (since this measurement is not used for analysis, there will be no centralized quality control measures implemented)	
832 833	 HbA1c level measured at a Central Lab from blood draw performed at Randomization Visit and 13-week Visit. 	
834	2. C-peptide/Glucose:	
835 836	 C-peptide with concurrent glucose level measured at a Central Lab from blood draw performed at Randomization Visit 	
837	3. Urine Pregnancy:	

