1371	 Insulin
1372	 Total daily insulin delivery
1373	 Percentage of insulin delivered as basal
1374	Weight change
1375	 Change in lipid levels
1376	Cardiovascular events
1377	• Patient-reported outcome (PRO) measures (see section 8.3)
1378	11.4.4 Safety Endpoints
1379	Severe hypoglycemia
1380	Diabetic ketoacidosis
1381	 Hyperosmolar hyperglycemic syndrome
1382	Other serious adverse events
1383	 Unanticipated adverse device effects
1384	• Hypoglycemia and prolonged hyperglycemia endpoints listed as effectiveness endpoints
1385	• Infusion set failures
1386	Other device malfunctions/device issues
1387	11.5 Analysis Datasets and Sensitivity Analyses
1388 1389 1390 1391	All analyses comparing the AID arm with Control arm will follow intention-to-treatment approach, which means participants will be analyzed in the treatment arm assigned by randomization regardless of actual system use. All randomized participants will be included in the primary analysis and secondary analyses of CGM metrics.
1392 1393	Safety outcomes will be reported for all enrolled participants, irrespective of whether the participant was randomized, or the study was completed.
1394	11.5.1 Per Protocol Analyses
1395 1396 1397	Per-protocol analyses will be performed for primary outcome and secondary hierarchical outcomes only if >5% of participants will be excluded. All of the following criteria must be met for a participant to be included in the per-protocol analyses. The criteria are as follows:
1398	• 13-week visit completed
1399	 No major protocol deviations

Device use: AID group - closed loop mode active for at least 80% of the time over the
 13-week period; control group - CGM use for at least 80% of the time over the
 visit period

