### 336 **5.8 Analysis Windows**

Analysis windows apply to the following outcomes measured at 13-week final visit:

- HbA1c
- Insulin (Control group only; see Section 5.6)
- Weight
  - Questionnaires
- 341 342

To be included in the corresponding analyses, these data must be collected between days 61 and 121 from the randomization. The target date is 91 days from the randomization.

345

This does not apply to the CGM or insulin metrics (AID group only) which are calculated as described above in Section 5.6.

348 349

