#### 476 **8.4. Sensitivity Analyses**

477 Confounding

A sensitivity analysis for the primary outcome, HbA1c, will also be conducted if potential confounding
factors collected at baseline are detected.

- The imbalance will be assessed based on clinical judgment reviewing the distributions in the two
  treatment arms, not on a p-value. The person making this judgement will be unaware of whether there is
  an association between baseline variables and study outcome.
- 483
- 484 Missing Data
- 485 Missing data will be handled using direct likelihood method for the primary analysis. It is worth noting 486 that all statistical methods for handling missing data rely on untestable assumptions and there is no one 487 correct way to handle missing data. Our goal is to minimize the amount of missing data so that the 488 results will not be sensitive to which statistical method is used.
- To that end, sensitivity analyses will be performed to explore whether results are similar for primaryanalysis when using different methods. The following methods will be applied:
  - Rubin's multiple imputation with treatment group in the imputation model
  - Available cases only
- Multiple imputation with pattern mixture model assuming the dropout trajectory of the AID group was that of the Control group (Mallinckrodt and Clark, 2003)
- Tipping point analysis to determine the magnitude of selective dropout bias necessary to alter conclusions of the study.
- 497

491

492

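### As written, the primary HbA1c model takes nothing from a participant missing either HbA1c value, and two of the four missing-data checks would largely repeat it

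*SAP*

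**What the plan says.** **Model.** SAP 7, like Protocol 11.6, analyses 13-week HbA1c with a linear mixed-effects "regression model adjusting for baseline HbA1c and clinical center (random factor"). A separate variance "will be modelled for each treatment group".

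**Data.** Protocol 8.1 has "HbA1c level measured at a Central Lab from blood draw performed at Randomization" and again at the 13-week visit. SAP 7 adds: "Only central lab HbA1c measurements will be used in the analyses". For the follow-up value, SAP 5.8 requires that "these data must be collected between days 61 and 121" from randomisation. Each person therefore has one baseline and at most one usable follow-up value.

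**Missing data.** SAP 7 says that direct likelihood will draw on baseline when the 13-week value is absent, and will work in a similar way when baseline is absent. SAP 6.2 states: "All randomized participants with any data will be included in the primary and secondary analyses", with partial data handled by maximum likelihood. Protocol 11.5 states: "All randomized participants will be included in the primary analysis".

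**Sensitivity analyses.** SAP 8.4 lists four: multiple imputation with treatment group in the imputation model; "Available cases only", not defined further; control-based pattern-mixture imputation; and a tipping-point analysis.

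**The concern.** Direct likelihood recovers information from incomplete participants when they have other values of the response. Here the model sentence puts baseline on the right-hand side and leaves a single response. A person without that response has nothing to contribute, so the model sentence conflicts with the sentences on missing data and on the analysis set.

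Two things are at stake. Two programmers could build different primary analyses from the same text. And the available-case analysis, offered as a check on the primary, may simply be the primary again. If AID participants who do poorly leave more often, the primary estimate would be too favourable and that check would agree with it.

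**Working it through.** **1. The plan's own figures.** SAP 4 gives SD 1.0, correlation 0.3, two-sided 5% and 300 completers; at 2:1 this is 200:100.
- Residual SD = 1.0 × √(1 − 0.3²) = 0.954.
- SE = 0.954 × √(1/200 + 1/100) = 0.117.
- Detectable difference at 90% power = (1.960 + 1.282) × 0.117 = 0.379, against the stated 0.38.
- Power is 90.2% at 0.38, 85.0% at 0.35 and 80.6% at 0.33, so all three stated points reproduce.

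These are completer figures. Ten per cent dropout from 220:110 leaves 198:99 = 297, with 89.9% power at 0.38.

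**2. The model as written.** Let y0 be baseline, y1 the 13-week value, and d the treatment effect. Each likelihood term is f(y1 | y0, arm, centre), with mean a + d·arm + b·y0 + centre.
- If y1 is missing, the term integrates to 1 and drops out. In a simulated trial with 33 missing outcomes, the log-likelihood was identical with 330 or 297 rows.
- If y0 is missing, the mean cannot be evaluated and the person is dropped. If 3% of baselines were also missing (assumed; 10 people), 287 would contribute.

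**3. The joint reading.** Write f(y0; μ0) × f(y1 | y0, arm, centre), with one baseline mean for both arms and centre entering the 13-week part.
- A person without y1 contributes only f(y0), which contains neither d nor b.
- With a common slope, the 13-week effect is (a + d + b·μ0) − (a + b·μ0) = d. This equals the complete-case estimate. Over 200 simulated trials the largest difference was 9 × 10⁻⁷, which is optimiser error.
- With arm-specific slopes, the effect is d + (b_AID − b_Control)·μ0, so baseline-only participants matter only through μ0. The largest difference was 0.030 (SD 0.008).
- With 3% of baselines also missing, 330 rather than 287 contribute, and estimates differ by up to 0.070 (SD 0.021).

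**4. Outcome-related dropout.** The simulation used 220:110, correlation 0.3, a true effect of −0.38, and dropout of about 10% or slightly less per arm. Three assumptions are not from the documents: selection acts in the AID arm only; AID dropout odds are 1.65 to 2.7 per SD of on-study glycaemia; and the partial correlation of mean CGM glucose with 13-week HbA1c is 0.5 to 0.7. Mean estimates over four scenarios, 2,000 trials each:

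| Analysis | Mean estimate |
|---|---|
| Full data, no dropout | −0.376 to −0.381 |
| Complete-case | −0.394, −0.408, −0.424, −0.442 |
| Baseline-only joint model, arm-specific slopes | same as complete-case |
| With on-study mean CGM glucose | −0.374 to −0.382 |

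Complete-case overstates the effect by about 0.02 to 0.06. Against the SE of 0.117, that is 0.02/0.117 = 0.17 to 0.06/0.117 = 0.51 standard errors. When the same selection was applied to both arms, the bias was at most 0.001.

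**5. The four checks.** The available-case analysis repeats the primary, exactly or nearly so unless baselines are missing. Multiple imputation from arm and baseline alone uses the same information as step 3, so it would largely repeat it too. The control-based and tipping-point analyses make different assumptions about dropouts and remain informative.

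**The case against.** The strongest reply is that the SAP does not commit to a complete-case analysis. Its sentence on a missing baseline, and the partial-data rule in SAP 6.2, make sense only if baseline is modelled as a response. A reader might infer from the model sentence that the primary analysis simply is complete-case; the documents do not settle that. This stands, and it makes the defect an inconsistency between sentences. But no section writes the joint model, its covariance or its baseline constraint, and step 3 shows that the choice hardly affects the estimate when only 13-week values are missing.

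A reader might also infer that intention-to-treat fails. Both documents define it as analysis by assigned arm whatever the system use, and that holds under either model. What fails, under the model as written, is the statement about who is included.

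Other parts of the reply also stand:
- Complete-case ANCOVA is unbiased if missingness depends only on baseline and arm.
- The simulated bias needs selection in one arm, and its parameters are assumed. Conditioning on CGM works well partly because dropout was made to depend on on-study glycaemia.
- Protocol 5.5 limits the loss. Those who stop AID are asked to stay to week 13, and early terminators from week 4 have the 13-week procedures, usable from day 61.
- SAP 8.4 does not exclude CGM from the imputation model. It names treatment group and gives no full list of variables.

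**Conclusion.** The point holds as a contradiction to resolve and a cheap improvement to make. As written, about 297 of 330 participants inform the primary estimate at the planned dropout, which conflicts with SAP 6.2 and Protocol 11.5. Two of the four missing-data checks would largely repeat the primary; the other two can still expose outcome-related dropout. No stated sample size or power figure changes.

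The possible overstatement of 0.02 to 0.06 rests wholly on the assumed AID-only selection and CGM correlation, and is not an estimate of what this trial will show. It might be inferred that rewriting the primary as a joint model would remove that bias. It would not: the joint model gave the same mean estimates as complete-case. The reduction came from the CGM data.

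**What to change.** - **SAP 8.4:** add on-study mean CGM glucose to the planned multiple-imputation model, alongside treatment group and baseline HbA1c. CGM is already uploaded at day 3 and at weeks 1, 4, 8 and 13 (SAP Table 2), and Protocol 5.5 asks those who stop AID to keep using it. State whether the SAP 5.3 definition applies, which removes challenge periods and requires 168 hours of data, and what is done for people below that minimum. Define the available-case analysis.
- **SAP 7, SAP 6.2 and Protocol 11.5:** state one of two things. Either baseline and 13-week HbA1c are modelled jointly as responses, with the baseline mean constraint, the covariance by arm and the place of centre written out; or the primary uses participants with both values. Align the three sections.

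The cost is wording and modest programming, with no new data. The benefit is limited to dropouts who have on-study CGM data.
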